As in the original design, the updated design is based on a bivariate decision curve, which formalizes the need to achieve a favorable balance between risk of srVTE and clinically relevant bleeding. This objective is even more critical in the context of the vulnerability of the pediatric population. Given this and given the logical hypothesis that bleeding will be reduced in children receiving shortened-duration anticoagulation, the updated statistical approach continues to employ a bivariate endpoint analysis (i.e., trade-off between srVTE and clinically relevant bleeding risks as described below). The bivariate decision curve is specified using 12-month risk difference or ARR for the srVTE and clinically relevant bleeding outcomes. The updated decision curve follows from the original decision curve as described in Section 1.3.

1.2 Statistical decision criteria using the bivariate (recurrent VTE:bleeding) outcome

1.2.1 Decision criteria for ARR in recurrent VTE and bleeding endpoints

[figure not shown]
A bivariate recurrent VTE:bleeding tradeoff curve for treatment effects measured by ARR was selected to have appropriate bivariate inference at 3 reference design points (Table 1, below): point A represents an important reduction in bleeding risk with a slight increase in srVTE risk, point B represents a smaller reduction in clinically relevant bleeding risk with no effect on srVTE risk, and point C indicates a slight increase in clinically relevant bleeding risk that is offset by a significant reduction in srVTE risk. As in any trial design, such reference points are selected because they represent effects that should engender appropriate decisions and statistical inference. Specifically, if there is evidence of a highly significant reduction in clinically relevant bleeding risk for the study intervention (shortened-duration anticoagulation), then a non-inferiority conclusion can be defended even if there is a slight increase in srVTE risk (point A: -12% bleeding risk reduction [95% confidence interval: -0.169 to -0.071] and 1% recurrent VTE risk increase [95% confidence interval: -0.039 to 0.059]). However, closer to the origin (point B), non-inferiority is decided when there is no difference in symptomatic recurrent VTE risk, but a slight reduction in clinically relevant bleeding risk. Although unlikely, point C represents a significant reduction in srVTE risk that offsets a 4% increase in clinically relevant bleeding risk.

Table 1. Statistical inference at the 3 reference design points on the Kids-DOTT decision curve assuming 285 subjects per group and 10% event risk.

Hypothetical Result	VTE risk difference		Bleed risk difference	
	Observed	95% CI	Observed	95% CI
A	0.01	(-0.039, 0.059)	-0.12	(-0.169, -0.071)
B	0.00	(-0.049, 0.049)	-0.04	(-0.089, 0.009)
C	-0.05	(-0.099, -0.001)	0.04	(-0.009, 0.089)

The methods of Kittelson et al. [1,2] are used to create a smooth curve through the three reference points to define bivariate decision criteria is given in Appendix equation (1) and is plotted in Figure 1.

Figure 1. Protocol-specified bivariate decision criteria for ARR for risk of srVTE and clinically relevant bleeding (Appendix equation 1).

[figure not shown]

1.3 Bivariate non-inferiority bound and trial power

The decision curve of equation (1) and [Figure 1](#) rejects the NI bound of equation (2) and is constructed under the assumption that srVTE and clinically relevant bleeding risks are both 10%. The curve must be shifted relative to the NI bound if the risks differ from 10%. Appendix equation (3) gives the equation for shifting the decision curve and is illustrated in [Figure 2](#).

1.3.1 Bivariate null hypothesis

Figure 2: Bivariate decision curve with lower event risk

A bivariate NI bound is needed in order to determine how the bivariate decision curve should shift if the observed variance differs from the pre-trial design. Specifically, the original bivariate decision curve of [Figure 1](#) is defined under the design assumption that the 12-month risks of srVTE and clinically relevant bleeding are both 10%. If the observed risks differ from these values, then the decision curve should shift relative to the NI bound. Equivalently, the standardized Z-score that is used to rule out the null curve should be the same regardless of the variance. The equations that define the NI bound and the final decision curve are given in the Appendix equations 1-3. [Figure 2](#) shows the NI bound (blue line), the decision curve of [Figure 1](#) (red line), and how that curve would shift if the 12-month srVTE event risk is 3% instead of 10%, and if the 12-month clinically relevant bleeding risk is 1% instead of 10%

(solid green line with 570 patients in the primary analysis population; dashed green line with 316 patients in the primary analysis population). The shift occurs because the variance of the ARR gets smaller as the risk gets closer to 0. The result is that with smaller variance the observed recurrent VTE-bleeding differences in the cross-hatched region would now lead to an NI decision. **Hence, with the lower variance associated with observed lower event risks than had been originally assumed based on historical data, there is a larger region of non-inferiority decision in the bivariate decision model, even if proposing a primary analysis population size that is smaller than initially proposed.** Power is therefore discussed further below.

1.3.2 Trial power

With bivariate decision criteria, the power of the trial must be evaluated using a bivariate probability distribution. [Table 2](#) shows the power for a non-inferiority decision of the bivariate design at the standardized mean treatment effects on srVTE and clinically relevant bleeding. [Table 3](#) shows the transformation of the standardized mean treatment effects into the ARR scale using different standard errors. The power from [Table 2](#) applies to the transformed effects in [Table 3](#).

Table 2: Power under the bivariate decision rule for standardized true mean effects

VTE Risk Difference (δ_V)	standardized effect on bleeding (δ_B)									
	-1.96	-1.64	-1.28	-0.84	0.00	0.84	1.28	1.64	1.96	
-1.96	0.979	0.955	0.909	0.813	0.512	0.203	0.103	0.050	0.024	
-1.64	0.974	0.949	0.896	0.793	0.482	0.185	0.089	0.043	0.021	
-1.28	0.966	0.938	0.875	0.765	0.450	0.160	0.076	0.036	0.016	
-0.84	0.951	0.913	0.842	0.717	0.394	0.132	0.059	0.027	0.012	
0.00	0.877	0.813	0.720	0.570	0.268	0.076	0.031	0.013	0.006	
0.84	0.690	0.612	0.503	0.363	0.144	0.033	0.012	0.005	0.002	
1.28	0.545	0.466	0.366	0.254	0.086	0.017	0.006	0.002	0.001	
1.64	0.411	0.345	0.262	0.170	0.054	0.010	0.003	0.001	0.000	
1.96	0.303	0.247	0.182	0.115	0.032	0.006	0.002	0.001	0.000	

Table 3: True mean difference between short and conventional duration therapy in different scales.

Scale	True mean difference on recurrent VTE or bleeding risks								
Standardized	-1.960	-1.645	-1.282	-0.842	0.000	0.842	1.282	1.645	1.960
¹ . S_{arr}	-0.049	-0.041	-0.032	-0.021	0.000	0.021	0.032	0.041	0.049
² . S_{arr}^V	-0.028	-0.024	-0.018	-0.012	0.000	0.012	0.018	0.024	0.028
³ . S_{arr}^B	-0.016	-0.014	-0.011	-0.007	0.000	0.007	0.011	0.014	0.016

¹. Assuming 10% event risk (standardized scale times 0.0251).

². Assuming 3% event risk (standardized scale times 0.0143).

³. Assuming 1% event risk (standardized scale times 0.0083).

As an example, using the decision curve of Appendix equation (1) the trial has 81.3% power under the hypothesis that there is no difference between short and standard duration therapy on the risk of symptomatic VTE recurrence ($\delta_V = 0$) and a 1.64 standardized reduction in the standardized mean effect on clinically relevant bleeding risk ($\delta_B = -1.64$). Assuming that the risk of srVTE is 3% and the true clinically relevant bleeding risk is 1%, then the trial has 81.3% power under the hypothesis that ARR for srVTE risk is 0 and ARR for clinically relevant bleeding risk is reduced by 1.4% (i.e., -1.64 times the standard error for bleeding, 0.0083). A reduction in the risk of srVTE and bleeding gives more power for the NI decision, as evidenced by the fact that the green lines in [Figure 2](#) are shifted to the northeast relative to the red line.

In addition to trial power, it is useful to evaluate the likely width of the 95% confidence interval upon trial completion. [Table 4](#) shows how the trial sample size affects the length for the srVTE and bleeding outcomes. As described above and illustrated [Figure 2](#), the critical value curve is determined by the size of the confidence rectangle (formed from the 95% confidence intervals for bleeding and srVTE). For example, with a total of 570 patients in the primary analysis population ([Figure 2](#) solid green line), the 95% confidence rectangle has total width of 5.6% horizontally and 3.2% vertically. If there are 316 patients in the primary analysis population, then the rectangle is 7.6% horizontally and 4.4% vertically ([Figure 2](#) dashed green line).

Table 4: Length (half-width) of 95% confidence interval as a function of sample size.

Number randomized	570	416	354	332	316	292	270
CI half-width for srVTE (3% risk)	0.028	0.033	0.036	0.037	0.038	0.039	0.041
CI half-width for bleeding (1% risk)	0.016	0.019	0.021	0.021	0.022	0.023	0.024

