2.3 Analysis of tertiary and exploratory endpoints

2.3.1 Analysis of subgroups

If there are a sufficient number of events, the ARR for the primary and secondary efficacy and safety endpoints will be calculated separately within each level of the stratification variables.

3. APPENDIX: Bivariate decision criteria

The bivariate decision curve for the design of Kids-DOTT was derived from the 3 reference points in **Table 1** that were selected to capture a clinically meaningful balance between the potential benefits of symptomatic recurrent VTE risk reduction and the potential for increased clinically relevant bleeding risk. The bivariate decision curve of **Figure 1** is given by equation (1) below, which is based on the standard error of the ARR (S_{arr}) assuming a 10% risk for recurrent VTE and a 10% risk for clinically relevant bleeding. The bivariate NI bound is given by equation (2), which is the curve that is shifted by 1.96 standard errors to the northeast of the decision curve. If the bleeding and VTE risks differ from the original assumptions, then the revised decision curve shifted by 1.96 standard errors to the southwest of the NI bound (equation 3). The shifted decision curve (**Figure 2**, green line) is given by equation (3) using a 3% risk of symptomatic recurrent VTE ($\pi_V = 0.03$) and a 1% risk of clinically relevant bleeding ($\pi_B = 0.01$).

$$\text{ARR decision curve: } (ARR_V - 0.025)(ARR_B - 0.08) = 0.003 \quad (1)$$

$$\text{ARR null curve: } (ARR_V - 0.025 - 1.96S_{arr})(ARR_B - 0.08 - 1.96S_{arr}) = 0.003 \quad (2)$$

$$\text{Shifted decision curve: } (ARR_V - 0.025 - 1.96S_{arr} + 1.96S_{arr}^V)(ARR_B - 0.08 - 1.96S_{arr} + 1.96S_{arr}^B) = 0.003 \quad (3)$$

where $S_{arr} = \sqrt{0.1 \times 0.9 \times 2/285} = 0.0251$, $S_{arr}^V = \sqrt{\pi_V \times (1 - \pi_V) \times 2/285}$, and $S_{arr}^B = \sqrt{\pi_B \times (1 - \pi_B) \times 2/285}$, where π_V and π_B denote the 1-year risk of recurrent VTE and clinically relevant bleeding, respectively.

REFERENCES

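### SAP Table 2 has its srVTE and bleeding axes exchanged: the stated 81.3% power is about 49% under equation (1), and it does not carry over to the 3%/1% risks

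*SAP*

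**What the plan says.** Table 2 in SAP section 1.3.2 ("Power under the bivariate decision rule for standardized true mean effects") puts the srVTE effect in rows and the bleeding effect in columns. The worked example reads it that way. At a zero srVTE effect and a bleeding effect of −1.64 standard errors, using Appendix equation (1), "the trial has 81.3% power under the hypothesis that there is no difference between short and standard duration therapy" on srVTE.

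Table 3 converts standardized effects to risk differences at 10%, 3% and 1% risk, and the SAP says that the power in Table 2 "applies to the transformed effects in" Table 3. For 3% srVTE and 1% bleeding risk it accordingly repeats the figure: "then the trial has 81.3% power under the hypothesis that ARR for srVTE risk is 0" and bleeding falls by 1.4 points. The following sentence says that lower risks give more power.

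Section 1.3.1 introduces a smaller analysis set ("dashed green line with 316 patients in the primary analysis population"). For that size the SAP gives a curve and interval widths but no power.

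Protocol section H (Data Analysis Plan) states 82% power with 285 per group at an observed srVTE increase of 1% and an observed bleeding decrease of 5%.

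**The concern.** The worked example sits almost on one of the SAP's own reference points. In section 1.2.1, "point B represents a smaller reduction in clinically relevant bleeding risk with no effect on srVTE risk"; Table 1 places it at srVTE 0 and bleeding −4%, on the decision curve. The example's true effect is srVTE 0 and bleeding −4.1%. When the truth lies on the decision boundary, the estimate falls on either side about equally often, so power should be near 50%, not 81%.

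The carry-over is doubtful for a different reason. Equation (3) moves the curve when the standard errors change but leaves the constant 0.003 in absolute units. The curve is then not the same on the standardized scale, so equal standardized effects need not have equal power.

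These are the power figures offered for the primary bivariate decision, and the SAP uses them in arguing that a smaller population is acceptable.

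**Working it through.** **Inputs.** V and B are the srVTE and bleeding risk differences.
- Equation (1), SAP Appendix: non-inferiority when V < 0.025, B < 0.08 and (V − 0.025)(B − 0.08) > 0.003.
- 285 per group (Table 1); 316 in total (section 1.3.1), taken as 158 per group.
- Standard errors from the Appendix formula √(π(1 − π)·2/n). For n = 285: S = 0.0251 at 10%, 0.0143 at 3%, 0.0083 at 1%. For n = 158: 0.0192 at 3%, 0.0112 at 1%.
- Correlation between the two estimates: not stated. Zero is assumed, and −0.5 to +0.5 was tried.

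**Is equation (1) itself right?** Yes. It passes through all three reference points:
- A: (0.01 − 0.025)(−0.12 − 0.08) = 0.0030
- B: (0 − 0.025)(−0.04 − 0.08) = 0.0030
- C: (−0.05 − 0.025)(0.04 − 0.08) = 0.0030

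**Power formula.** With threshold v*(b) = aV − 0.003/(aB − b), power is the integral over b < aB of Φ((v*(b) − μV)/SV) times the normal density of b with mean μB and standard deviation SB. For equation (1), aV = 0.025, aB = 0.08 and SV = SB = 0.02513.

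**Step 1: Table 2 against equation (1).**

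| True effect (standard errors) | Table 2 | Equation (1) |
|---|---|---|
| srVTE 0, bleeding −1.64 | 0.813 | 0.487 |
| srVTE −1.64, bleeding 0 | 0.482 | 0.801 |

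A simulation of 4 million draws gives 0.487 and 0.801. Over all 81 cells:
- As labelled, the largest difference is 0.48, and 60 cells differ by more than 0.02.
- Transposed, the largest difference is 0.032, and 13 cells differ by more than 0.02.
- At correlation −0.2, every transposed cell agrees within 0.003, while the labelled reading is still off by up to 0.487.
- Over correlations from −0.5 to +0.5, the example's power stays between 48.4% and 49.4%.

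One check needs no integration. Equation (1) requires an estimated V below 0.025. With no true srVTE effect, power cannot exceed Φ(0.025/0.02513) = 84.0%, whatever bleeding does. Table 2 as labelled shows 87.7% at srVTE 0 and bleeding −1.96.

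**Step 2: carry-over to 3%/1% risks.** Equation (3) has aV = 0.025 + 1.96(S − SV) and aB = 0.08 + 1.96(S − SB), still with 0.003. The srVTE threshold at an observed bleeding difference of zero is aV − 0.003/aB:

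| Curve | aV | aB | Threshold | In srVTE standard errors |
|---|---|---|---|---|
| Equation (1), 285 per group | 0.0250 | 0.0800 | −0.0125 | −0.50 |
| Equation (3), 285 per group | 0.0462 | 0.1129 | 0.0197 | +1.38 |
| Equation (3), 158 per group | 0.0366 | 0.1073 | 0.0087 | +0.45 |

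The standardized boundary moves, so the power must be recomputed. With a true srVTE difference of zero:

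| True bleeding difference | 285 per group | 158 per group |
|---|---|---|
| −1.64 standard errors | 94.1% (−1.4 points) | 74.3% (−1.8 points) |
| −1.4 points | 94.1% | 72.7% |
| 0 | 91.2% | 66.7% |

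**Step 3: the protocol's 82%.** Read as an observed result, the point fails equation (1): (0.01 − 0.025)(−0.05 − 0.08) = 0.00195, below 0.003. Read as true effects at 10% risks, power is 36.3%. Exchanging the axes gives 79.6%, which is close to 82% but does not prove the cause.

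**Secondary check, exact rule.** SAP section 2.1.3 decides with exact intervals against equation (2). An independently written version of that rule (not the R package the SAP names) was run with srVTE at 3% in both arms and the two endpoints independent. With bleeding at 0.3% versus 1.7%, it gives about 87% (285 per group) and 54% (158 per group). With bleeding at 1% in both arms, it gives about 81% and 44–45%.

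**The case against.** The axis exchange is hard to dispute, but several points limit what follows from it.

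- **The SAP never states 81.3% for 316 patients.** Table 3 uses the 285-per-group standard errors. At that size and 3%/1% risks, the stated figure is below what equation (3) gives (81.3% against 94.1%). This stands: for 316 the defect is an omission. A reader looking for power at that size will still find only 81.3%.
- **The equation (3) figures are not power under the actual decision rule.** They use a normal approximation with few events, whereas the decision uses exact intervals. This stands, and the exact-rule check suggests that 74% is optimistic.
- **The 74% uses a bleeding effect of −1.8 points.** At the SAP's own −1.4 points it is 72.7%. Both are shown above.
- **The protocol's sentence mixes observed values, a critical value and power.** The 36% therefore holds only if its effects are read as true effects. This stands: the firm conclusion there is that 82% is not reproducible.
- **Nothing operational changes.** The primary database was locked in March 2021 (protocol section I), and the decision rule is correct. That limits the harm, but the figures are still wrong as written and describe how informative the design was.

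**Conclusion.** The point holds. At the SAP's worked example, equation (1) gives 48.7% power, not 81.3%. Table 2 matches equation (1) only with its axes exchanged, and no correlation from −0.5 to +0.5 rescues the labels. Carrying 81.3% over to the 3%/1% risks is also wrong. Equation (3) gives 94.1% with 285 per group. With 158 per group it gives 72.7% at −1.4 points, 74.3% at −1.8 points and 66.7% with no bleeding difference.

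These figures assume a normal approximation, independent estimates and equal allocation; the exact rule is likely to give less. Confidence is high for Table 2 and for both 81.3% statements. It is moderate for the protocol's 82%, whose method is not stated.

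**What to change.** In SAP section 1.3.2:
- Exchange the axis labels of Table 2 or, better, recompute the table. State the correlation used: relabelling alone would leave values that fit a correlation near −0.2, which the SAP does not mention.
- Correct the equation (1) example to about 48–49%.
- Withdraw the statement that Table 2 power transfers through Table 3. Replace it with power computed from equation (3) at 285 and 158 per group, for named absolute true differences that include a bleeding difference of zero.
- Report power under the exact-interval rule of section 2.1.3 beside these figures.

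In protocol section H, replace the 82% with a recomputed power at stated true effects and risks, and keep observed critical values separate from true effects.

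The cost is wording and a short calculation, with no new patients or data and no change to the decision rule. The equation (1) and protocol figures become less favourable, and the 316-patient power, once stated, falls below 81.3%. The equation (3) figure for 285 per group at 3%/1% becomes more favourable.

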Given that duration of anticoagulation in VTE reflects a balance between efficacy (symptomatic recurrent VTE) and safety (clinically-relevant bleeding) as defined in the Primary Outcome Measures section above and given the hypothesis that bleeding will be reduced in children receiving shortened-duration anticoagulation, the statistical analysis will employ a bivariate endpoint analysis (i.e., trade-off approach). With a sample size of 285 per group in the randomized population, there is 82% power to conclude non-inferiority at an observed absolute increase in recurrent VTE of 1% (i.e., critical value of 1%, 95% CI upper bound of $<6\%$), with an observed absolute decrease in clinically significant bleeding of 5%. Accounting for an estimated rate of persistently occlusive thrombosis of 15% at 6 weeks (randomization exclusion), and an anticipated non-retention rate of 25% for the primary endpoint at 1 year follow-up, a **total randomized population of 420 participants is targeted to meet study goals of a total of 316 participants in the primary analysis population (1 year follow-up primary endpoint)**. Based on most recent randomization rates (28 June 2019) we estimate a total enrollment of 609 in the randomized and observational components of the Kids-DOTT study. The bivariate endpoint analysis statistical function for the completed trial is graphically depicted in **Figure 2**. The methods used to define the bivariate decision curve are described in the SAP. The SAP also describes how the decision curve changes when the event rate differs from the pre-trial design.

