2.1.3 Analysis methods for primary endpoints

The primary efficacy analysis will estimate/test the ARR for clinically relevant bleeding and symptomatic VTE recurrence. The ARR and 95% confidence intervals will be estimated using the exact methods of Fay et al.[3] using the R package exact2x2. Non-inferiority will be decided if the 95% confidence rectangle rules out the non-inferiority curve defined by Appendix equation (2). Note that the exact confidence intervals of Fay et al. will result in a discrete decision curve instead of the smooth curve illustrated by the lines in Figure 2. The primary analysis will use data from the PP population, but the ITT analysis will also be conducted and reported as confirmatory.

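### SAP Table 4 gives normal-approximation interval widths as the likely final precision, but the exact intervals planned in SAP 2.1.3 are expected to be about 22% (srVTE) and 49% (bleeding) wider at 316 analysed

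*SAP*

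**What the plan says.** SAP 1.3.2 introduces Table 4 by saying "it is useful to evaluate the likely width of the 95% confidence interval upon trial completion". The table lists 95% half-widths at seven sample sizes, for a 3% risk of symptomatic recurrent VTE (srVTE) and a 1% risk of clinically relevant bleeding. The text above it turns two columns into confidence rectangles. For 570 patients it gives 5.6% by 3.2%, and for the reduced size it says "If there are 316 patients in the primary analysis population, then the rectangle is 7.6% horizontally and 4.4% vertically". The same paragraph says that the size of this rectangle determines the critical curve.

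The analysis section names a different interval: "The ARR and 95% confidence intervals will be estimated using the exact methods" of SAP reference 3, using the R package exact2x2. Non-inferiority is decided by whether the rectangle from those intervals rules out the curve of Appendix equation (2). SAP 2.1.3 notes that exact intervals make the decision curve discrete. It does not say that they are wider than Table 4.

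The sample-size row of Table 4 is labelled "Number randomized". The text above the table calls 570 and 316 the primary analysis population, and Protocol IV.H (Data Analysis Plan) says that a "total randomized population of 420 participants is targeted to meet study goals of a total of 316 participants in the primary analysis population".

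**The concern.** Table 4 and the 7.6% by 4.4% rectangle are the SAP's statement of the precision that remains when the analysed population falls from 570 to 316. If they rest on an interval that the analysis will not use, the reader is told of more precision than the trial can expect. A normal approximation is weakest with few events, and here 158 × 0.03 = 4.7 recurrences and 158 × 0.01 = 1.6 bleeds are expected per arm. Because the rectangle drives the decision, the difference could also alter which observed results appear to support non-inferiority.

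**Working it through.** **Inputs.** Risks of 3% and 1% and the sample sizes come from SAP Table 4. Equal allocation follows from the design basis in SAP 1.2.1, "assuming 285 subjects per group and 10% event risk", so 316 analysed is 158 per arm and 570 is 285 per arm. The interval method is from SAP 2.1.3. The non-inferiority curve and S_arr = 0.0251 are from the SAP Appendix.

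**Step 1: reproduce Table 4.** The formula is half-width = 1.96 × √(2p(1−p)/n), with n per arm.

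- 316, srVTE: 1.96 × √(2 × 0.03 × 0.97/158) = 0.0376 (printed 0.038).
- 316, bleeding: 1.96 × √(2 × 0.01 × 0.99/158) = 0.0219 (printed 0.022).
- 570: 0.0280 and 0.0163 (printed 0.028 and 0.016).

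All 14 cells reproduce this way, so Table 4 is Wald throughout and contains no slip of arithmetic.

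**Step 2: the planned interval.** The melded exact interval for a difference of two proportions combines the one-sample Clopper-Pearson limits of each arm, taken as beta confidence distributions. It was coded directly in Python because exact2x2 was not available. Half the interval length was averaged over binomial event counts in both arms, with equal true risks of 3% (srVTE) and 1% (bleeding).

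| Analysed | srVTE, Wald | srVTE, exact | Bleeding, Wald | Bleeding, exact |
|---|---|---|---|---|
| 570 | 0.0280 | 0.0324 | 0.0163 | 0.0217 |
| 416 | 0.0328 | 0.0390 | 0.0191 | 0.0269 |
| 316 | 0.0376 | 0.0460 | 0.0219 | 0.0328 |
| 270 | 0.0407 | 0.0508 | 0.0237 | 0.0368 |

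At 316 the excess over Wald is 0.0460/0.0376 = 1.22 and, from unrounded values, 0.03279/0.02194 = 1.49. At 570 it is 16% and 33%. Doubling the half-widths gives expected rectangles of about 9.2% by 6.6% at 316 and 6.5% by 4.3% at 570.

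Single outcomes at 158 per arm agree. For srVTE, 5 v 5 events give 0.0475. For bleeding, 1 v 1 gives 0.0302 and 2 v 2 gives 0.0356.

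**Step 3: effect on the decision.** In equation (2) the asymptotes are 0.025 + 1.96 × 0.0251 = 0.0743 for srVTE and 0.08 + 1.96 × 0.0251 = 0.1293 for bleeding. The rectangle rules out the curve when its upper corner lies below both asymptotes and the product of the two distances exceeds 0.003. With no observed difference, the corner equals the half-widths:

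- 316, Wald: (0.0743 − 0.0376) × (0.1293 − 0.0219) = 0.0039 > 0.003, so non-inferior.
- 316, mean exact: (0.0743 − 0.0460) × (0.1293 − 0.0328) = 0.0027 < 0.003, so not shown.
- 570, mean exact: (0.0743 − 0.0324) × (0.1293 − 0.0217) = 0.0045 > 0.003, so non-inferior.

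In actual counts at 158 per arm, 5 v 5 recurrences fail with 1 v 1 bleeds (0.00265) and with 2 v 2 bleeds (0.00251). With 4 v 4 recurrences and 1 v 1 bleeds the rule is only just met (0.003002).

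Averaged over outcomes with equal true risks of 3% and 1%, the probability of a non-inferiority decision at 316 is about 0.68 with Wald intervals (standard errors from observed rates) and 0.45 with exact intervals. At 570 it is about 0.91 and 0.81.

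**The case against.** Four points can be made for the plan.

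- **Table 4 is a planning approximation.** It is computed consistently with the standard errors in Table 3 and the Appendix. That stands, and it is why this is a mismatch of method and not an arithmetic error. But the SAP offers the table as the likely width at completion, and the completed trial will report a different interval.
- **The final decision does not use Table 4 or the green curves.** It uses the exact rectangle computed from the data. That also stands. A reader might infer that the primary analysis is invalid; SAP 2.1.3 does not support that.
- **SAP 2.1.3 already says that the smooth curves in Figure 2 will not hold exactly.** It discloses discreteness only, not the extra width.
- **A less conservative exact interval would narrow the gap.** A mid-p version gives about 0.040 for 4 v 5 recurrences and 0.027 for 1 v 2 bleeds, roughly 6% and 24% above Wald. The SAP does not mention mid-p.

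A reader might also infer that the row label, or the use of the per-protocol set, adds to the understatement, or that the 416 column describes the roughly 420 randomised patients. Neither reading holds. SAP 1.3.1 and 1.3.2 and Protocol IV.H all treat 316 as the number analysed, the stated rectangle is already on that number, and the SAP never applies the 416 column to this plan. The whole gap comes from Wald versus exact.

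**Conclusion.** The precision stated in SAP 1.3.2 is too favourable for the analysis planned in SAP 2.1.3. At 316 analysed, the exact half-widths are expected to be about 0.046 and 0.033, not 0.038 and 0.022. That is an excess of 22% and about 49% over the Wald values; put as a shortfall from the exact width, it is 18% and 33%. These percentages belong to 316 only.

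The result assumes equal arms, equal true risks of 3% and 1%, and the standard (non-mid-p) melded interval. The 9.2% by 6.6% rectangle is an expectation; the realised one will depend on the event counts.

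A reader might go further and conclude that the SAP's claim of a larger non-inferiority region than under the 10% design is lost. It is not: the expected exact half-widths at 316 (0.046 and 0.033) are still below the 0.049 of the 10% design, though only narrowly for srVTE. What does not survive is the impression that, at 316, a result of no difference on either endpoint would typically suffice. The row label is a separate, minor inconsistency.

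**What to change.** Recompute every Table 4 entry, and the 570- and 316-patient rectangles, as expected widths of the interval named in SAP 2.1.3, and state the assumed risks. On the assumptions above the rectangles become about 6.5% by 4.3% and 9.2% by 6.6%.

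For Figure 2, mark the green curves as normal approximations that show a larger non-inferiority region than the exact rule allows. Alternatively, replace them with the region, or the probability of a non-inferiority decision, computed under the exact rule at 316. Redrawing them from average exact widths would not be enough, because the exact limits depend on the observed counts.

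Separately, relabel the Table 4 row as the number in the primary analysis population, to agree with the SAP text and Protocol IV.H.

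The cost is one table, one paragraph and one figure or its caption. Eligibility, treatment and the analysis method do not change. The downside is that the stated precision at 316 looks less favourable.
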